8.1.4 Adverse Events Requiring Hospitalization

If a subject is treated in a medical facility (hospital, emergency room, free-standing clinic) related to the occurrence of any AE, the following data will be collected to model health care utilization in patients with Dravet syndrome: AE/reason for hospitalization/clinic visit; duration of the visit in hours/days; admission to intensive care unit; and name/number of procedures performed, including but not limited to, electroencephalogram, ECG, ECHO, positive emission tomography (PET) scan, magnetic resonance imaging (MRI), x-ray, computed tomography CT) scan, surgery, and lumbar puncture/spinal tap.

8.2 SEVERITY OF ADVERSE EVENTS

The severity of AEs (whether nonserious or serious AEs) is to be assessed by the investigator as follows (Table 11).

Confidential Page 75 of 182

Table 11: Severity Definition of Adverse Events

Severity	Definition		
Mild:	A type of AE that is usually transient and may require only minimal treatment or therapeutic intervention. The event does not generally interfere with usual activities of daily living.		
Moderate:	A type of AE that is usually alleviated with additional specific therapeutic intervention. The event interferes with usual activities of daily living, causing discomfort but poses no significant or permanent risk of harm to the research participant.		
Severe:	A type of AE that interrupts usual activities of daily living, or significantly affects clinical status, or may require intensive therapeutic intervention.		
CDISC SDTM Severity Intensity Scale for Adverse Event Terminology			

8.3 CAUSALITY OF ADVERSE EVENTS

The causal relationship of an AE to IMP must always be assessed by the investigator. All AEs will be classified as either **related** or **not related** to IMP. If a causality assessment is not provided for an AE (including an SAE), that AE will be considered as related to IMP.

The degree of certainty with which an AE is attributed to IMP or an alternative cause (e.g., natural history of the underlying disease, concomitant medication) will be determined by how well the event can be understood in terms of:

- Known pharmacology of ZX008
- Clinically and/or pathophysiologically plausible context
- Reaction of a similar nature previously observed with similar products, or reported in the literature for similar products as being product related (e.g., headache, facial flushing, pallor)
- Plausibility supported by the temporal relationship (e.g., the event being related by time to administration or termination of treatment with IMP drug withdrawal or reproduced on rechallenge)

The following classifications should be used in categorization of relatedness:

Not Related: Concomitant illness, accident or event with no reasonable association with study drug.

Confidential Page 76 of 182

Related:

The event follows a reasonable temporal sequence from administration of study drug and is definitive pharmacologically; cannot to be attributed to concurrent disease or other factors or medications. A clinically reasonable response should be observed if the study drug is withdrawn or dose reduced.

8.4 OBSERVATION PERIOD FOR ADVERSE EVENT REPORTING

The observation period for AE and SAE reporting in an individual subject will start at the time of giving written informed consent for participation in the current study and finish 15 days after the last dose of study drug or the last visit, whichever is later. For subjects who enroll in the openlabel extension study, ongoing AEs will be followed in that study.

If the investigator becomes aware of an SAE that has started after the observation period has finished, and the event could in some way be associated with IMP (irrespective of whether or not it is considered by the investigator to be causally related to IMP), then this must also be reported to the sponsor (see Section 8.6).

8.5 ADVERSE EVENT REPORTING

8.5.1 Adverse Events

At each clinical evaluation, the investigator (or delegate) will determine whether any AEs have occurred. Adverse events will be recorded in the AE page of the eCRF. If known, the medical diagnosis of an AE should be recorded in preference to the listing of individual signs and symptoms. The investigator must follow up on the course of an AE until resolution or stabilization. If an AE is ongoing after the end of study visit, the AE will continue to be followed up until resolution or stabilization.

If, during the study period, a subject presents with a pre-existing condition that was not noted at the time of study entry, the condition should be retrospectively recorded in the Medical History section of the eCRF.

8.6 SERIOUS ADVERSE EVENTS REPORTING

This study will comply with all applicable regulatory requirements and adhere to the full requirements of ICH Topic E2A (Clinical Safety Data Management: Definitions and Standards for Expedited Reporting [1994]).

In the event of a SAE the investigator or delegate must:

- 1. Enter all relevant information in the AE page of the eCRF
- 2. Inform the Medical Monitor or the Sponsor of the SAE via email or telephone within 24 hours of becoming aware of the SAE.
- 3. Follow the initial notification with a completed SAE report form. The SAE form must be emailed or faxed to iHC within 24 hours of becoming aware of the SAE.

All SAEs that occur during the course of the study, beginning the day Informed Consent is

Confidential

Page 77 of 182

signed, whether or not causally related to IMP must be reported immediately via telephone or email (within 24 hours of the investigator becoming aware of the event) to the sponsor or the Medical Monitor.

Adverse events occurring in the period between the time the subject gave written informed consent and the first exposure to IMP that meet one or more of the seriousness criteria for AEs must be reported to the sponsor and the Medical Monitor in the same manner as other SAEs and will be included in the clinical study database.

Any SAE that occurs 15 days after the last dose of study drug or the last visit, whichever is later that is considered to be causally related to IMP must be reported immediately (i.e., within 24 hours of the investigator becoming aware of the event) to the sponsor and the Medical Monitor.

Contact details and guidance for reporting SAEs will be provided to study site before the study starts.

8.6.1 Requirements for Immediate Reporting of Serious Adverse Events

The minimum reporting requirements for immediate reporting of SAEs include:

- 1. Identifiable subject
- 2. Suspected drug product
- 3. Event description
- 4. Identifiable reporting source

In addition, the investigator must:

- 1. Report all SAEs to the relevant IRB/IEC within the timeframe specified by the IRB/IEC.
- 2. Submit follow-up reports to the sponsor Global Clinical Safety and Pharmacovigilance and the Medical Monitor until the SAE has resolved, or, in the case of permanent impairment, until stabilized.
- 3. Ensure that the AE term(s) and causality assessment for all SAEs is entered in the eCRF.

If the minimum requirements for reporting are fulfilled, the investigator should not wait to receive additional information to fully document the event before notifying the sponsor.

When submitting SAE reports to the sponsor, subjects should be identified only by their subject number and study number. The investigator should not include the subject's name and address.

SAE Update reports can be submitted to the sponsor any time that additional relevant information becomes available. In cases of death, the investigator should supply the sponsor and the IEC/IRB (as applicable, see Section 8.7) with any additional requested information as it becomes available (e.g., autopsy reports and detailed medical reports). Once an SAE is reported to the sponsor's Safety Group, a Safety Specialist may contact the investigator with follow-up questions.

Confidential Page 78 of 182

The procedure to be followed if an ongoing AE becomes an SAE after the end of the observation period for AEs is described in Section 8.9.

8.7 REPORTING OF SERIOUS ADVERSE EVENTS BY INVESTIGATOR TO IEC/IRB

The timeframe within an IEC/IRB must be notified of a death or an unexpected SAE considered at least possibly related to the IMP is stipulated by each individual IEC/IRB. The investigator is responsible for complying with the requirements for IEC/IRB notification. The investigator will notify the relevant IEC/IRB within the applicable timeframe by forwarding the safety report (e.g., MedWatch/CIOMS form) completed by the sponsor for the notifiable event.

8.8 REPORTING OF EVENTS OTHER THAN SERIOUS ADVERSE EVENTS BY INVESTIGATOR TO SPONSOR

Even if none of the criteria for an SAE are fulfilled, any of the following events must be reported by the investigator to the Medical Monitor within 72 hours from the time the investigator is notified.

- 1. Hypersensitivity reactions
- 2. Pulmonary hypertension
- 3. Cardiac symptoms requiring intervention, or valvulopathy, if identified outside of study-related monitoring

8.9 FOLLOW-UP OF ADVERSE EVENTS

Every effort should be made to follow-up subjects who continue to experience an AE or an SAE on completion of the study or until the AE resolves. All follow-up information (and attempted follow-up contacts) should be documented in the subject's medical records. Details of the subject's progress should also be submitted to the sponsor's Global Clinical Safety and Pharmacovigilance and the Medical Monitor. In the event of a SAE a blood sample for ZX008 and AED PK should be collected as soon as feasible.

Subjects who are discontinued from the study or complete the study and have been found to have any signs of valvulopathy or pulmonary hypertension on ECHO will be followed until the condition has resolved or stabilized where no further changes are likely, for a minimum of

6 months from the last dose of study medication, unless it is determined after unblinding that the subject did not receive ZX008.

8.9.1 Follow-up of Echocardiogram Findings

All ECHOs will be evaluated by a central reader from BioMedical Systems, Inc. (BMS), in consultation with the IPCAB, if warranted. Findings related to pulmonary hypertension or valvulopathy on any of the four valves (aortic, mitral, pulmonary, triscuspid) will be reported to the investigator with grades of normal, trace, mild, moderate or severe. If the ECHO result has

Confidential Page 79 of 182

progressed in severity since the last reading then new oversight measures will be enacted as described below in Levels 1-3. Table 11 describes the severity of ECHO findings with the level of increasing oversight if the subject is to remain in the study.

Table 12: Clinical Measures Enacted Upon Increasing Severity of ECHO Findings

	Valve			
Severity	Aortic	Mitral	Pulmonary	Tricuspid
Normal	Level 1	Level 1	Level 1	Level 1
Trace	Level 2	Level 2	Level 1	Level 1
Mild	Level 2	Level 2	Level 1	Level 1
Moderate	Level 3	Level 3	Level 3	Level 3
Severe	Level 3	Level 3	Level 3	Level 3

Level 1: Continue per protocol

Level 2.

- 1. If there is a desire to continue study medication:
 - a. The investigator will evaluate the efficacy to date based on study diaries and consult with the parent/guardian, and determine whether study treatment was associated with significant, meaningful benefit in number, severity and/or duration of seizures and/or on the impact on daily functioning.
 - b. The investigator will consider whether the subject has had reasonable trials (dose and duration) of other available anticonvulsants (e.g. valproic acid, clobazam, or topiramate), alone or in combination, and not maintained the level of seizure control achieved with study medication.
- 2. If the investigator feels consideration of continued treatment is warranted considering benefit and potential risk, and the parent/guardian feels strongly that the child be maintained on the study medication when understanding the risks, the parent/guardian must sign a new consent which describes the additional risk and the child should provide assent if appropriate.
 - a. If both of these conditions are not met, the subject is discontinued from treatment.
- 3. The investigator prepares a case history and rationale for continuation to be submitted to the IDSMC for review, including consideration of effects on seizures and comorbidities.
- 4. The Co-Chairs of the IPCAB are alerted to the request and prepare, after consultation with BMS, an evaluation of the cardiopulmonary risk and proposed monitoring plan if applicable, for submission to the IDSMC.
- 5. IDMSC will review the submission from the Investigator and the IPCAB and unblind the subject treatment if warranted.
- 6. IDSMC makes a determination of appropriate path, including the possible outcomes:

Confidential Page 80 of 182

- a. Discontinue study medication
- b. Increase frequency of ECHO and ECG monitoring
- c. Add additional ECG and/or ECHO measures to be monitored
- d. Reduce the dose of study medication

Level 3:

- 1. The investigator will evaluate efficacy to date based on study diaries and consult with the parent/guardian, and determine whether the achieved benefit justifies the consideration of continuing study treatment by the IDSMC. MINIMAL efficacy criteria for IDSMC consideration:
 - a. Seizures must be more than 75% improved (number of convulsive seizures per 28 days) on treatment over baseline, and improvement must be consistent.
 - b. The number, type, duration, and distribution of seizures at baseline should be of a severity, which justifies the risks of cardiopulmonary complications, considering the subject's age and overall health.
 - c. Subject has had reasonable trials (dose and duration) of other available anticonvulsants (e.g., valproic acid, clobazam, topiramate), alone or in combination, and not maintained the level of seizure control achieved with study medication.
- 2. If the investigator feels consideration of continued treatment is warranted considering benefit and potential risks, and the parent/guardian feels strongly that the child be maintained on the study medication when understanding the risks, the parent/guardian must sign a new consent, which describes the additional risks and the child should provide assent if possible.
 - a. If both of these conditions are not met, the subject is discontinued from treatment.
- 3. The investigator prepares a case history and rationale for continuation to be submitted to the IDSMC for review, which includes effects of study medication on seizures and comorbidities related to Dravet syndrome.
- 4. The Co-Chairs of the IPCAB are alerted to the request, and in consultation with BMS prepare an evaluation of the risks and proposed monitoring plan if applicable for submission to the IDSMC.
- 5. IDSMC will review the submission from the Investigator and the IPCAB and unblind the subject treatment if warranted.
- 6. IDSMC makes a determination of appropriate path, including these possible outcomes:
 - a. Discontinue study medication
 - b. Increase frequency of ECHO and ECG monitoring
 - c. Add additional ECG and/or ECHO measures to be monitored
 - d. Reduce the dose of study medication

Confidential Page 81 of 182

8.10 PREGNANCY

This study is open to female and male subjects. Whenever possible, a pregnancy in a female subjects or the female partner of a male subject exposed to IMP should be followed to term so as to assess any potential occurrence of congenital anomalies or birth defects. Any follow-up information, including premature termination and the status of the mother and child after delivery, should be reported by the investigator to the sponsor using a pregnancy reporting/outcome form.

9. DATA HANDLING PROCEDURES

9.1 RECORDING OF DATA

The investigator (or delegate) will maintain individual records for each subject. These records should include dates when a subject visited the study site, study-required information and data, and other notes as appropriate. These records constitute source data.

An eCRF and a subject diary will be provided by the sponsor (or delegate) for each subject enrolled into the study. Study site staff will enter data directly into the validated electronic data capture (EDC) system by completing the eCRF via a secure internet connection. The investigator is responsible for ensuring accurate and proper completion of the eCRF and subject diary for recording data according to the instructions given in the eCRF and subject diary.

All entries in the eCRF must be backed up by the relevant source data at the study site. All source data will be kept according to all applicable regulatory requirements (see Section 12.8). Source data must be completed legibly for each subject enrolled into the study and signed by the investigator (or delegate).

Data entry in the eCRF and subject diary must be completed in a timely manner so that they always reflect the latest observations on the subjects enrolled in the study.

The subject's diary will be completed by the parent/caregiver at home. Data entries will be reviewed by the investigator for completion and consistency.

9.2 DATA QUALITY ASSURANCE

An initiation meeting will be held before starting the study, during which the study design, procedures to be followed, and measures for ensuring standardized performance will be explained by a delegate from the sponsor, and a common understanding of the requirements of the study will be reached with the investigator and other relevant personnel at the study site.

Data generated throughout the study will be monitored and the data entered in the eCRFs will be checked against the subject records for completeness and accuracy. The sponsor's study monitor will perform this function.

The computer system used for study data handling will be fully FDA 21 CFR Part 11 compliant. All creation, modification or deletion of electronic study records will be documented through an automated Audit Trail. Following completion of eCRF pages and entry of the data into a Confidential

Page 82 of 182

database, the data will be checked electronically for consistency and plausibility. Data queries will be generated for questionable data and response clarification will be sought from the investigator. These data queries must be resolved in a timely manner by the investigator (or delegate).

9.3 RECORD RETENTION

A study document binder will be provided by the sponsor for the investigator at each site for all requisite study documents (constituting the "Investigator Study File").

Following completion of the study, the investigator will retain copies of the approved study protocol, ICF, relevant source documents, and all other supporting documentation related to the study according to applicable regulatory requirements.

The investigator is responsible for archiving the Investigator Study File, the subject's records, and the source data according to applicable regulatory requirements. These documents have to be archived for at least 15 years or at least 2 years after the last approval of a marketing application in an ICH region, but should be retained for longer if required by regulatory requirements or by agreement with the sponsor.

If the investigator can no longer maintain the archive of study records (e.g., due to retirement or relocation), the sponsor must be informed in writing about any change in responsibility for record retention, including the name of the new responsible party, contact information, and location of the study records. Records may not be destroyed without prior written consent from the sponsor.

10. STATISTICS

10.1 DETERMINATION OF SAMPLE SIZE

The results of the only randomized, placebo-controlled studies in subjects with Dravet syndrome can be found in the European Public Assessment Report (EPAR) for stiripentol (EMA, 2007). The EPAR summarizes the results from two studies: STICLO France and STICLO Italy. In the stiripentol groups, the SD of the percentage change in seizure frequency from baseline to month 2 was 42% in the French trial and 26% in the Italian trial. The analogous SDs for placebo groups were 38% and 62%. An SD of 50% was assumed for the primary analysis in this trial comparing ZX008 0.8 mg/kg/day to placebo on the change from baseline in seizure frequency. Using a two-sided test at the α =0.05 significance level, a sample size of 35 subjects per treatment group affords 90% power to detect a difference in mean change from baseline of 40 percentage points. Similar assumptions and calculations yield a requirement for an additional 35 subjects in the 0.2 mg/kg/day ZX008 group. Thus, the total sample size is planned to be 105 subjects (35 per arm).

10.2 ANALYSIS POPULATIONS

10.2.1 Safety (SAF) Population

All safety analyses will be performed on the SAF Population defined as all randomized subjects

Confidential

Page 83 of 182

who receive at least one dose of ZX008 or placebo. Subjects will be analyzed according to the treatment actually received.

10.2.2 Modified Intent-to-Treat (mITT) Population

The mITT Population is defined as all randomized subjects who receive at least one dose of ZX008 or placebo and for whom at least one week of diary data are available. Subjects will be analyzed according to the treatment group to which they were randomized. The primary comparison of ZDX008 0.8 mg/kg/day to placebo, as well as key secondary analyses, will be performed on the mITT Population.

10.2.3 Per Protocol (PP) Population

The PP Population is defined as all randomized subjects who receive at least one dose of ZX008 or placebo, complete the entire 12 week Maintenance Period, and have no major protocol deviations that would have a significant impact on clinical outcome. Subjects will be analyzed according to the treatment they received. The primary and key secondary efficacy analyses will be repeated on the PP Population if there are substantial differences in the makeup of the mITT and PP Populations.

10.3 TREATMENT GROUPS

Subjects will be randomly assigned to one of three treatment groups: ZX008 0.8 mg/kg/day, ZX008 0.2 mg/kg/day, or placebo.

10.4 TREATMENT PERIODS

Baseline Period

The Baseline Period covers the approximately 42-day span just prior to randomization and the start of treatment. The baseline frequency of convulsive seizures will be calculated from data collected during this period.

Titration Period

The Titration Period covers the first 14 days of treatment while subjects are titrated to their randomized dose. It begins on the first day of treatment (Study Day 1) and extends through Study Day 15 regardless of the exact day on which a subject reaches his or her assigned dose. The Titration Period applies to all subjects including placebo recipients.

Maintenance Period

The Maintenance Period covers the 12 weeks following the end of the titration period. It begins on Study Day 16 and extends through Study Day 99.

Titration + Maintenance (T+M) Period

The T+M period combines the Titration and Maintenance periods, beginning on Study Day 1 and extending through Study Day 99. The T+M period is considered the treatment period.

Confidential Page 84 of 182

Follow-up Period

The Follow-up Period begins immediately at the end of T+M period and extends to a final visit 2 weeks later; i.e., from Study Day 99 through Study Day 113. Only subjects who do not roll over enrollment into the open-label extension will participate in the Follow-up Period.

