- b: Subjects who are discontinued early and those who complete the study and choose not to enroll in the separate open-label extension will be tapered off study medication over an up to 2-week period.
- c: Follow-up ECG, ECHO, and physical examination will be performed 3-6 months after early termination, or for those subjects who complete the study but do not enter the open-label extension study (see Section 6.4).
- d: The Visit 8 ECHO must be performed any time between Study Day 40 and Study Day 54. The Visit 12 ECHO must be performed any time between Study Day 90 and Study Day 113; if a subject discontinues early from the study, the ECHO should be scheduled as soon as practical. If the Study Day

Confidential Page 23 of 182

- 43 ECHO was completed < 30 days prior to early termination, the Visit 12 ECHO will not be performed provided the parent/guardian agrees to bring the subject to the clinic for the cardiac follow-up visit.
- e: Females of child-bearing potential
- f: Plasma sample for pharmacokinetic assessment will be conducted prior to the dose at Visit 8 and 1, 2, and 4-6 hours after dose administration.
- g: Plasma sample for assessment of background AED(s) will be conducted prior to the dose of AED(s) at Visits 3, 6, 8 and 12.
- h: Study drug/diary dispensed for the Transition Period for subjects entering the open-label extension study and for the Taper Period for subjects exiting the study.
- i: Site personnel will review study medication dosing procedure (titration) with parent/caregiver.
- j: Study drug administration begins in the morning of Study Day 1.
- k: Only adverse events related to cardiac safety will be collected at this visit.
- l: Mandatory one time collection any time during or after screening.

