Subjects who complete the Maintenance Period and will be continuing into the open-label extension study will be transitioned from double-blind study medication to open-label ZX008 (Table 5). Study medication will be administered as equal doses BID in the morning and in the evening approximately 12 hours apart, with food. Each dose should be separated by a minimum of 8 hours and a maximum of 12 hours. A missed dose of study medication may be taken later up to 8 hours before the next scheduled dose; otherwise, the missed dose should not be given. Study medication should be administered using the oral dosing syringe provided.

All subjects entering the open-label extension study will be transitioned from their blinded daily dose (placebo, 0.2 mg/kg/day, 0.8 mg/kg/day, or 30 mg/day) to the 0.2 mg/kg dose during the 2-week interval between Visits 12 and 13, without breaking the blind. The IVR/IWR system will assign two bottles of IMP to the subject, one for each step in the transition. A new bottle of IMP will be started by the subject at each level of the transition step. See Section 5.6 for more information about the volume of ZX008 or placebo to be administered.

Table 5: **Transition Algorithm**

Dose Group in Double-Blind Study	Transition Step 1 Day 1-4 after Visit 12	Transition Step 2 Days 5-14 after Visit 12	
ZX008 0.2 mg/kg/day	ZX008 0.2 mg/kg/day	ZX008 0.2 mg/kg/day	
ZX008 0.8 mg/kg/day	ZX008 0.4 mg/kg/day	ZX008 0.2 mg/kg/day	

Confidential Page 47 of 182

Placebo	ZX008 0.2 mg/kg/day	ZX008 0.2 mg/kg/day		
Note: maximum daily dose of ZX008 is 30 mg.				

Subjects who had been randomized to placebo increase their dose to 0.2 mg/kg/day beginning on Day 1 of the transition (the day following Visit 12). Subjects who had been randomized to 0.2 mg/kg/day will continue to receive that dose. Subjects who had been randomized to 0.8 mg/kg/day or were receiving the maximum dose of 30 mg/day decrease to a dose of ZX008 0.4 mg/kg/day, or a maximum of 30 mg/day. After 4 days at this dose level (Day 5), these subjects will decrease their dose to 0.2 mg/kg/day. Subjects will report to the clinic on Day 15 for enrollment into the open-label extension study.

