6. VISIT SCHEDULE

Study procedures will be conducted according to the Schedule of Assessments in Table 1. Time windows for all assessments are detailed in Table 6.

Table 6: Time Windows for Assessments

Visit / Procedure	Time window (relative to scheduled visit / procedure)
Visit 1 (Clinic; Study Day -43 to -42 or -42 to -41):	Not applicable
Visit 2 (Phone; Study Day -21)	± 3 days
Visit 3 (Clinic; Study Day -1; Randomization)	+ 4 days ^a
Visits 4, 5 (Phone: Study Days 4, 8)	± 3 days
Visit 6 (Clinic; Study Day 15)	± 4 days
Visit 7 (Phone: Study Day 29)	± 4 days
Visit 8 (Clinic; Study Day 43)	± 4 days

Confidential Page 50 of 182

Visit 9 (Phone: Study Day 57)	± 4 days
Visit 10 (Clinic; Study Day 71)	± 4 days
Visit 11 (Phone: Study Day 85)	± 4 days
Visit 12 (Clinic: Study Day 99)	± 4 days
Visit 13 (Clinic; Study Day 113; post dosing)	± 4 days
Visit 14 (ECHO clinic; 3-6 months after last dose)	+ 30 days
Blood collection for ZX008 PK	± 15 minutes
Blood collection for AED concentration	Prior to morning dose of AED medication

AED=antiepileptic drug (s); ECHO=echocardiogram; PK = pharmacokinetics

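### T+M ends at a fixed Study Day 99 although Visit 12 may fall on Days 95–103; separately, the Visit 12 ECHO window lets a placebo subject's ECHO follow up to 14 days of ZX008

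*Protocol*

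**What the plan says.** Section 10.4 fixes the periods by calendar day. Of Maintenance it says: "It begins on Study Day 16 and extends through Study Day 99". Of the combined period: "The T+M period combines the Titration and Maintenance periods, beginning on Study Day 1 and extending through Study Day 99". Neither is tied to the subject's own Visit 12 or last dose at the randomised level.

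Table 6 in Section 6 gives "Visit 12 (Clinic: Study Day 99) ± 4 days". Section 5.5.5 (Transition Period) has subjects "randomized to placebo increase their dose to 0.2 mg/kg/day beginning on Day 1 of the transition (the day following Visit 12"), while those on "0.8 mg/kg/day or were receiving the maximum dose of 30 mg/day decrease to a dose of ZX008 0.4 mg/kg/day". Subjects not entering the extension start the taper on the first day after completion (Section 5.5.4, Table 4). There the 0.8 mg/kg/day arm steps down and the 0.2 mg/kg/day arm moves to placebo.

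A diary is dispensed for the transition or taper (Table 1, footnote h). Section 10.5.1.1 calculates the mean convulsive seizure frequency (MCSF) from all available data in the Baseline or T+M Periods, and Section 10.2.2 analyses subjects as randomised.

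For echocardiography, Table 1 footnote d says "The Visit 12 ECHO must be performed any time between Study Day 90 and Study Day 113", and Section 6.2.9 repeats this. Section 10.5.2 summarises ECHO results by treatment. Section 10.2.1 analyses the safety population by treatment actually received.

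**The concern.** The analysis window is anchored to a nominal day and the change of treatment to a visit that can move by four days either way. Applied as written, the rule labels some days with a treatment the subject was no longer taking and discards some days on which the subject was still taking it. This touches the primary endpoint and every key secondary endpoint computed over T+M.

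The ECHO window raises a second problem with its own cause. It runs two weeks past the nominal end of Maintenance, and nothing requires the ECHO to precede the first transition dose. Placebo subjects moving to the extension take ZX008 in those two weeks. Valve disease and pulmonary hypertension are the reason the protocol gives in Section 1.2 for the product's withdrawal, so an unexposed placebo reference matters for the cardiac comparison.

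**Working it through.** **The plan's own figure.** Section 10.1 uses SD 50, a difference of 40 percentage points and two-sided α = 0.05, and states 35 per arm for 90% power. By the normal approximation n = 2(1.960 + 1.282)² × 50² / 40² = 32.8, so 33. Power at 35 is 91.7% (91.0% with the noncentral t). The stated figure holds and serves here only as a yardstick.

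**Days misassigned.** Let V be the study day of Visit 12 (95–103, Table 6). Transition or taper starts on V + 1 and T+M ends on Day 99.

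- Post-switch days counted in T+M = max(0, 99 − V)
- Randomised days left out of T+M = max(0, V − 99)

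| Visit 12 day | Post-switch days inside T+M | Randomised days dropped |
|---|---|---|
| 95 | 4 (4/99 = 4.0%) | 0 |
| 96 | 3 | 0 |
| 97 | 2 | 0 |
| 98 | 1 | 0 |
| 99 | 0 | 0 |
| 100–103 | 0 | 1–4 |

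Against the 84-day Maintenance Period alone, four days are 4/84 = 4.8%.

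**Size in the efficacy comparison.** Assume every placebo subject enters the extension, is seen on Day 95, and gains the full effect E from the first transition dose. The placebo mean then shifts by E × 4/99: 0.4 points at E = 10, 1.6 at E = 40 and 2.4 at E = 60.

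- A difference of 40 becomes 40 − 1.6 = 38.4, and power at 35 per arm goes from 91.7% to 89.5%.
- If the 0.8 mg/kg/day arm also lost its whole effect on those four days, the difference is 40 − 2 × 1.6 = 36.8 and power is 86.8%.
- A milder assumption is that V is spread evenly over Days 95–103 and all placebo subjects roll over. The mean is (4 + 3 + 2 + 1)/9 = 1.1 days, or 1.1% of T+M. The shift is about 0.45 points and power about 91.1%.

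The first two are upper bounds.

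**ECHO.** With Visit 12 exactly on Day 99, the transition covers Days 100–113, so an ECHO on Day 113 falls on transition day 113 − 100 + 1 = 14. With Visit 12 on Day 103 the count is 113 − 104 + 1 = 10. With Visit 12 on Days 95–98 all 14 transition days can precede the ECHO. The exposure therefore arises even when Visit 12 is on time.

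**Period lengths in Section 10.4.**

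- Titration is described as the first 14 days but extends through Day 15, which is 15 days.
- Maintenance, Days 16–99, is 84 days, which is 12 weeks.
- T+M, Days 1–99, is 99 days, against the 14 weeks (98 days) in Sections 3.1 and 3.3.
- Follow-up starts on Day 99, so that day lies in two periods. Follow-up also excludes subjects entering the extension, so the transition belongs to no analysis period.

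**The case against.** Most of the case on the other side concerns size and cause, and much of it stands.

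- The efficacy effect is small. Four days needs Visit 12 on Day 95, and placebo subjects take ZX008 only if they enter the extension. Section 4.8 ordinarily requires the entire 12-week Maintenance Period for that. Read strictly, this conflicts with a Visit 12 on Days 95–98, but Section 4.8 also allows case-by-case entry and does not mention the visit window. The bias is conservative.
- A reader might infer that the Day 99 cut-off causes the ECHO problem. It does not. An ECHO on Days 100–113 is outside T+M by date, and ending T+M at Visit 12 would leave it where it is. The cause is the Day 90–113 window.
- A reader might also infer that early stoppers' taper and off-drug days necessarily enter T+M and make up a large share of it. The documents do not establish this. The Synopsis and Section 3.1 place taper after early discontinuation, as post-dosing follow-up, and Section 4.5 speaks of data collected until discontinuation. Placebo early stoppers taper on placebo. Counting such days as randomised could also be a legitimate treatment-policy choice. What remains is that the protocol does not say which rule applies.
- Table 7 requires no post-treatment ECHO after less than 2 weeks of treatment, which suggests that short exposure matters little. However, 14 days reaches its 2-to-4-week column, where one is required.
- Per-subject end dates are often left to the SAP, which is not shown. That would answer a gap, but here the protocol fixes an end date that conflicts with its own visit window.

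**Conclusion.** The point holds in three limited parts.

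1. The fixed Day 99 end misassigns up to four days per completer in either direction. The efficacy bias is toward no difference: at most about 1.6 points, or 3.2 if the 0.8 mg/kg/day arm also lost its whole effect on those days. Both bounds assume an immediate 40-point effect and every placebo subject seen on Day 95, on the percentage-point scale of the sample size section. This does not threaten the primary conclusion.
2. Separately, the Visit 12 ECHO of a placebo subject entering the extension can follow up to 14 days of ZX008, and no rule keeps it out of the placebo reference. The treatment-received rule does not say how a planned placebo-to-ZX008 switch is labelled. The effect of such exposure on ECHO findings cannot be sized from the document, but any effect would blur the between-arm cardiac comparison. This is the more important part.
3. The period definitions disagree by one day and overlap on Day 99.

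These should be corrected before unblinding, so that nobody has to decide afterwards which days and ECHOs count as placebo.

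**What to change.** - End Maintenance and T+M for each subject at the actual Visit 12 date (the last day on the randomised maintenance dose) or at early discontinuation, and use those days as the MCSF denominator. No transition day then falls in T+M, and the denominator for completers runs from 95 to 103 days.
- State whether diary days after early discontinuation count toward T+M, and run the other choice as a sensitivity analysis.
- In the between-arm ECHO summary, flag every ECHO done after the first transition or taper dose. Do not count a placebo subject's ECHO after the first ZX008 dose as unexposed placebo. Show results with and without the late ECHOs.
- Use one consistent day count for Titration, Maintenance, T+M and Follow-up, and reconcile Section 10.4 with Table 6, Section 4.8, Section 5.5.5 and Table 1 footnote d.

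The cost is protocol and SAP wording; no dose, visit or procedure changes. Some late ECHOs, in any arm, move to a separate display (the documents give no basis for how many), and follow-up length differs slightly between subjects.
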